### **Secondary endpoints**

The analyses will be conducted in the AS, overall and by treatment group (conservative group, invasive group). Descriptive statistics and within-group comparative analyses could be done by subgroup of conservative treatment (venoactive drugs, compression, combination of both), or by subgroup of invasive treatment (sclerotherapy, foam sclerotherapy, surgery, thermal ablation (laser or radiofrequency), non-thermal ablation, and venous stenting), if relevant.

Descriptive statistics will be provided for patient characteristics at V0 (in terms of demographics, profession, clinical characteristics, personal and family history of CVD, treatment history, specific comorbidities), risk factors, concomitant treatment and description of treatment characteristics per visit in terms of type of treatment (initial referral from GP and whether they actually received the treatment), concomitant treatment, compliance (for conservative treatment group only).

The proportion of patients who received an intervention as secondary/add-on treatment to conservative treatment (in the conservative treatment group) and the proportion of patients who received a re-intervention (in the invasive treatment group) and number of re-interventions will be provided. If there is enough recurrence (minimum 20% of concerned patients), a Kaplan-Meier analysis could be considered. Time to event will be calculated from the start date of conservative treatment to the date of the secondary/add-on intervention in the conservative treatment group.

Time-to-re-intervention will be calculated from the date of the intervention to the date of the re-intervention in the invasive treatment group.

Patients who will reach the end of the study without receiving an intervention (in the conservative group) or a re-intervention (in the invasive treatment group) will have the time to event censored at the date of treatment discontinuation for any other cause (in the conservative group) or at the date of the end of the study if study ended (in conservative and invasive treatment group).

The change in the CIVIQ-20 GIS over time from V0 to each follow-up visit will be evaluated with the same methods as the primary endpoint.

The change in the clinical part of the CEAP classification over time from V0 to each follow-up visit will be described.

The change in the rVCSS over time from V0 to each follow-up visit will be evaluated with the same methods as the primary endpoint.

The change in the symptomatology over time from V0 to each follow-up visit will be evaluated with the same methods as the primary endpoints.

The satisfaction score over time from V1 to each follow-up visit will be described as a quantitative variable.

Number and proportion of patients with AEs will be described.

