## 4. Study objectives and Design

### 4.1 Study objectives

The **primary objective** is to assess the evolution of the QoL after 12 weeks for patients with CVD who underwent conservative or invasive treatment.

The **secondary objectives** are:

1. To describe patient characteristics by treatment group, including demographic characteristics, clinical characteristics and specific comorbidities at the inclusion visit (V0), and risk factors and treatment characteristics per visit.
2. To estimate the proportion of patients who received an intervention as secondary/add-on treatment to conservative treatment or who received a re-intervention, and the time to secondary/add-on intervention or re-intervention.
3. To assess the evolution of the QoL over time by treatment.
4. To assess the evolution of the clinical part of the Clinical Etiological Anatomic Pathophysiologic (CEAP) classification over time by treatment.
5. To assess the evolution of patient’s signs through physician-assessed revised Venous Clinical Severity Score (rVCSS) over time by treatment.
6. To assess the evolution of patient’s assessment of symptom severity over time by treatment.
7. To assess the evolution of patient satisfaction over time by treatment.

8. To assess QoL, signs, symptoms and patient satisfaction of patients who received an intervention as secondary/add-on treatment to conservative treatment.
9. To assess the safety of treatments in patients with CVD.

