A delay between referral to the venous centre during the V0 and the day of invasive treatment is anticipated. To allow assessment of the primary study objective, GPs will be asked to invite the patients for a follow-up visit 12 weeks after the invasive treatment took place (V-i), provided that it falls within the scope of routine medical practice in terms of visit frequency.

Due to the real-world setting, patients might not be assessed exactly at the proposed weeks/months. Therefore, some visits may not take place if they are not within the scope of regular medical practice. Additionally, a time range around the visits will be allowed. The frequency of follow-up visits is upon the discretion of the treating physicians.

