### **9.2 Sample size**

Considering a Minimum Clinically Important Difference (MCID) of 5 points before/after treatment for the primary endpoint (CIVIQ-20 GIS), a default correlation of 0.5, and with an expected drop-out of 60% of patients in the conservative group and 25% in the invasive group, we propose the recruitment of 1650 patients (safe margin), to finally include minimally 1590 patients (power 90%).

Each investigator (120 GPs) will recruit approximately between 10 and 15 consecutive patients.

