### 9.3.2 Population for analyses

The following analysis population will be considered:

- Included Set (IS): This set corresponds to all patients included for the study and with an Informed Consent Form (ICF) signed.
- Analysis Set (AS): This set corresponds to all patients from the IS with at least one follow-up visit (i.e. with at least a date of visit completed for visits V1, V2, V3).

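### The inclusion-visit part of objective 1 is described only in patients who came back (AS), although the data exist for every included patient and the Included Set has no analysis assigned to it

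*Protocol*

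**What the plan says.** Objective 1 in Section 4.1 starts "To describe patient characteristics by treatment group, including demographic characteristics, clinical characteristics and specific comorbidities at the inclusion visit (V0" and goes on to risk factors and treatment characteristics per visit. It therefore has a V0 part and a per-visit part.

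Section 9.3.2 defines two sets. For the IS: "This set corresponds to all patients included for the study and with an Informed Consent Form (ICF) signed". For the AS: "This set corresponds to all patients from the IS with at least one follow-up visit", specified as "with at least a date of visit completed for visits V1, V2, V3". I read this as any one of the three visits. V4, V5 and V-i are not listed.

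Section 9.3.3, Secondary endpoints, opens with "The analyses will be conducted in the AS, overall and by treatment group (conservative group, invasive group". The next paragraph, under the same heading and with no other set named, says "Descriptive statistics will be provided for patient characteristics at V0 (in terms of demographics, profession, clinical characteristics" and includes the GP's initial referral. No analysis in Section 9.3 is assigned to the IS.

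Section 6.1 and Table 1 place demographics, history, comorbidities, risk factors and the GP's initial prescription or referral at V0. Section 5 asks for consecutive patients where possible so that the sample is representative. Section 4.4.2 accepts that "some visits may not take place if they are not within the scope of regular medical practice". Section 9.2 assumes "an expected drop-out of 60% of patients in the conservative group and 25% in the invasive group".

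**The concern.** A description of patients at inclusion needs no follow-up. Tying it to a later visit adds a selection step after enrolment, and that step depends on routine practice and on the patient. The table then shows who came back, while objective 1 asks who was included.

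Two things are at stake:

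- **Representativity.** Consecutive recruitment is the protocol's own safeguard, and the condition of returning weakens it.
- **Attrition.** Section 9.1 names attrition bias, but its only remedy is trying to contact lost patients. If V0 data are shown only for the AS, a reader cannot see whether non-returners differed at baseline.

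If return rates also differ between conservative and invasive patients, the treatment mix in the overall column changes as well.

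**Working it through.** **1. Which items need follow-up**

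| Item of objective/endpoint 1 | Collected | Needs a later visit? | Set in Section 9.3.3 |
|---|---|---|---|
| Demographics, history, comorbidities | V0 | No | AS |
| Risk factors at V0 | V0 | No | AS |
| GP's initial prescription or referral | V0 | No | AS |
| Treatment actually received, its start and type | V1-V5, V-i | Yes | AS |
| Compliance, later risk factors | V1-V5, V-i | Yes | AS |

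The first three rows are the mismatch. The last two fit the AS.

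**2. Possible effect on the overall column**

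The protocol gives no AS size and no conservative:invasive mix, so it has no figure of its own to reproduce here. I use the 1590 of Section 9.2 only as a scale. It cannot be rebuilt from the protocol, which states no standard deviation, and the percentages below do not depend on it.

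Inputs:
- Drop-out 0.60 conservative and 0.25 invasive (Section 9.2).
- *p* = invasive share of included patients (assumed).
- *s* = fraction of the stated drop-out that occurs before any V1-V3 visit (assumed, 0 to 1).

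Formula: invasive share in the AS = p(1 − 0.25s) / [p(1 − 0.25s) + (1 − p)(1 − 0.60s)].

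For p = 0.5:
- s = 0: 0.5 / 1 = 50.0%
- s = 0.25: 0.46875 / (0.46875 + 0.425) = 52.4%
- s = 0.5: 0.4375 / (0.4375 + 0.35) = 55.6%
- s = 1: 0.375 / (0.375 + 0.20) = 65.2%

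Other mixes:

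| True share p | s = 0 | s = 0.25 | s = 0.5 | s = 1 (upper bound) |
|---|---|---|---|---|
| 20% | 20% | 21.6% | 23.8% | 31.9% |
| 30% | 30% | 32.1% | 34.9% | 44.6% |
| 50% | 50% | 52.4% | 55.6% | 65.2% |
| 70% | 70% | 72.0% | 74.5% | 81.4% |

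Patients missing from the V0 tables at p = 0.5, out of 1590: 0, 169, 338 and 676 for s = 0, 0.25, 0.5 and 1 (for example 1590 × (1 − 0.575) = 676).

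**3. The opposite direction**

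The AS definition does not list V-i, and Table 1 lets V-i replace an overlapping visit. Let *v* be the extra fraction of all invasive patients left out of the AS because their only early visit is labelled V-i. Invasive loss is then 0.25s + v and conservative loss is 0.60s. The mix is unchanged when v = 0.60s − 0.25s = 0.35s, which is 8.75% at s = 0.25, 17.5% at s = 0.5 and 35% at s = 1. Above that value the overall column shifts towards conservative patients.

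**The case against.** The strongest reply has four parts.

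- **Much of endpoint 1 needs follow-up.** Treatment received and compliance cannot be described without a later visit. If groups follow treatment received, a patient who never returns cannot be classified. This stands for the per-visit items, which belong in the AS. It does not reach the V0-only items.
- **The SAP may add an IS table.** The general considerations in Section 9.3.3 promise summaries of all variables without naming a set, and leave group rules and planned tables to the SAP. That is fair, and the absence of a comparison table in the protocol is not in itself an error. But the protocol does name a set for the secondary endpoints, and that set excludes non-returners.
- **Describing the analysed population at baseline is legitimate.** It is, as an addition. It does not replace a description of the included population.
- **Baseline CIVIQ-20, CEAP, rVCSS and symptom scores are not part of objective 1.** This also stands: they belong to endpoints 3 to 6. They are useful for comparing patients in and not in the AS, but the mismatch with objective 1 does not concern them.

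A reader might infer from the 60% and 25% that the overall results certainly move towards invasive patients, and by a sizeable minimum. The protocol does not support this. It does not say when drop-out occurs, and a patient counted as a drop-out may still have attended a V1-V3 visit and so be in the AS. The V-i omission can act in reverse.

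**Conclusion.** The point holds for the V0-only items. As written, the plan removes included patients from a description that needs nothing beyond V0, and it leaves the IS without a use. This does not depend on the direction or amount of drop-out, only on some patients having no dated V1-V3 visit, which the protocol itself anticipates.

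The change in mix is conditional. At an assumed 50:50 mix it lies between 0 and about 15 percentage points towards invasive, if early loss is proportional to the stated drop-out. It can be smaller or reversed if invasive patients seen only at V-i fall outside the AS. It affects the overall columns only. The by-group tables have no mix to shift, although each may still be selected for patients who returned. The primary analysis is not affected. This is a low-cost improvement to objective 1 and to the assessment of attrition.

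**What to change.** In Section 9.3.3, Secondary endpoints:

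1. State that the V0-only items of objective 1 (patient characteristics, V0 risk factors, GP's initial prescription or referral) are described in the IS, overall and by V0 prescription or referral. Label the grouping as such, because it can differ from the treatment received.
2. Add a table of V0 characteristics and baseline scores for IS patients in and not in the AS.
3. Keep per-visit treatment characteristics, treatment actually received, compliance and all change-from-V0 analyses in the AS.

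The cost is one sentence and one or two extra tables from data already collected. The downside is a grouping by referral that may not match the AS grouping, so the two sets of tables need clear titles.

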### 5.3 Expected duration of study

The end of the study is defined as 2 years after the first visit of the last patient included (Last Patient First Visit [LPFV]). The total duration of the study will be 2 years and half (6 months of inclusion + 2 years of follow-up).

Patients have the right to withdraw from the study at any time and for any reason without prejudice for their future medical care. Patients can withdraw their consent without the need to justify their decision. In case of consent withdrawal, data collection will stop from the date of consent withdrawal.

Patients will be considered lost to follow-up if the investigator is not able to contact them despite multiple attempts. In case of study withdrawal, the reason for discontinuation should be recorded. The sponsor has the right to prematurely discontinue the study if the decision is justified.

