### **Within-group comparisons**

Within group differences will be evaluated by a paired t-test, a Wilcoxon signed-rank test or a linear mixed model with random intercepts (on the raw data or the rank data depending on the distribution of the variable of interest) for continuous variables. In case of categorical variables, McNemar's test or Cochran's Q test will be used according to the number of modalities of the variable.

Time-to-event endpoints will be expressed in weeks. For the description, Kaplan-Meier estimates (product-limit estimates) will be presented with a summary of associated statistics (number of events, number of censored data / median, Q1 and Q3 survival time / estimate rates of patients not presenting the event of interest at 6 weeks, 12 weeks, 6 months, 12 months and 24 months) including the corresponding two-sided 95% CIs. The Kaplan-Meier curve will also be presented.

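### Time to add-on intervention or re-intervention: the 20% gate on Kaplan-Meier contradicts the general methods and is harder to pass as drop-out rises, and censoring at treatment discontinuation distorts the estimate

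*Protocol*

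**What the plan says.** Secondary endpoint 2 (Protocol 4.3) includes the proportion of patients with an add-on intervention or a re-intervention and the time to that event.

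Protocol 9.3.3 treats the time component in two places. Under Within-group comparisons it says of time-to-event endpoints: "For the description, Kaplan-Meier estimates (product-limit estimates) will be presented", with rates from 6 weeks to 24 months. Under Secondary endpoints it says: "If there is enough recurrence (minimum 20% of concerned patients), a Kaplan-Meier analysis could be considered". The proportions themselves are to be provided in every case.

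The censoring rule, also under Secondary endpoints, applies to "Patients who will reach the end of the study without receiving an intervention (in the conservative group) or a re-intervention (in the invasive treatment group". In the conservative group these patients "will have the time to event censored at the date of treatment discontinuation for any other cause (in the conservative group". A second date is offered for both groups, and it is the only one named for the invasive group: "or at the date of the end of the study if study ended (in conservative and invasive treatment group".

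Section 5.3 adds two relevant statements: "The end of the study is defined as 2 years after the first visit of the last patient included" and "Patients will be considered lost to follow-up if the investigator is not able to contact them despite multiple attempts". Section 9.2 sizes the study "with an expected drop-out of 60% of patients in the conservative group and 25% in the invasive group".

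**The concern.** There are two problems with rules that the protocol states.

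First, this is the only time-to-event endpoint in the protocol, so the general promise of Kaplan-Meier can refer to nothing else. The specific text then makes that same analysis conditional on the data and optional even when the condition is met. The condition is set on observed events. Patients who leave early have less time in which an event can be seen, so drop-out pushes the observed share down. The heavier the loss, the more likely it is that the crude proportion, which ignores loss, is the only result reported. The two groups have different expected drop-out, so the same true rate could pass the gate in one and fail it in the other.

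Second, stopping conservative treatment is not leaving the study. Patients are followed for two years and intervention status is recorded at every follow-up visit (4.4, Table 1). Censoring them when treatment stops discards follow-up that bears directly on the question of who goes on to an intervention.

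**Working it through.** **Inputs from the protocol.** Drop-out d = 60% (conservative) and 25% (invasive), Section 9.2, with no time horizon. Follow-up of 24 months per patient, Section 4.4. Gate of 20%, Section 9.3.3. The protocol states no event rate or precision for this endpoint, so there is no figure of its own to reproduce.

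**Assumptions.** True 24-month rate p from 20 to 40%; exponential event times; drop-out independent of the event and spread evenly over 24 months.

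**Step 1: the crude share that the gate sees.** Let Λ = −ln(1 − p). Patients who stay contribute p(1 − d). Patients who leave contribute d times the average of 1 − exp(−Λt/24) over t from 0 to 24, which is d(1 − p/Λ). So

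crude = p(1 − d) + d(1 − p/Λ).

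For p = 25% and d = 60%: Λ = 0.2877; 1 − 0.25/0.2877 = 0.131; crude = 0.25 × 0.40 + 0.60 × 0.131 = 0.100 + 0.079 = 0.179.

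| True 24-month rate | Crude, 60% drop-out | Crude, 25% drop-out |
|---|---|---|
| 20% | 14.2% | 17.6% |
| 25% | 17.9% | 22.0% |
| 30% | 21.5% | 26.5% |
| 40% | 29.0% | 35.4% |

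Setting crude = 20% and solving for p, the gate is passed only when the true rate exceeds about 27.9% at 60% drop-out and 22.7% at 25%. With exponential instead of even drop-out, these thresholds are 29.7% and 22.9%. At 60% drop-out and a true 25%, a simulated Kaplan-Meier estimate with lost patients censored at last contact returns 25.0%.

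**Step 2: censoring at discontinuation, literal reading.** The rule covers only patients who never have an intervention. Someone who stops treatment and later has an intervention therefore counts as an event, while event-free patients leave the risk set when they stop. If a share s of event-free patients stops evenly over 24 months, the risk set at t is exp(−Λt/24) − (1 − p)·s·t/24. The estimate is 1 − exp(−∫ f(t)/[risk set at t] dt) from 0 to 24, with f(t) = (Λ/24)exp(−Λt/24). For p = 25%:

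- s = 20%: 27.2%
- s = 40%: 30.2%
- s = 60%: 34.4%

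The bias is upward because membership of the risk set depends on what happens later.

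**Step 3: censoring at discontinuation, ordinary reading.** Here everyone is censored on stopping and later interventions are ignored. Simulation gives:

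- True 25%, stopping unrelated to the event: 25.0%, no bias.
- True 25%, half of those heading for an intervention stop one month before it, and 20% of patients stop for unrelated reasons: about 13.5%.
- Base rate 30%, 60% stopping by 24 months, hazard doubled after stopping: true 37.6%, estimate 29.8%.
- Same, hazard halved after stopping: true 25.4%, estimate 30.0%.

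On this reading the direction depends on why patients stop.

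**The case against.** Four points can be made on the other side.

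- **The SAP may settle the date for lost patients.** A reader might infer that patients lost to follow-up are carried as event-free to study end. Kaplan-Meier would then equal the crude proportion (about 18% for a true 25% at 60% drop-out). The protocol does not say this. Its rule is limited to patients who reach the end of the study, and it is silent on the others. That silence is a detail an SAP can fill and is not held against the plan here. The objection does not reach the gate or the discontinuation rule, which the protocol states itself.
- **The discontinuation rule need not understate.** A reader might infer that it hides interventions and so lowers the rate. Read literally, the rule still counts them and the bias is upward; on the other reading the direction is open. Only the need to change the rule stands.
- **The inputs are soft.** The 60% belongs to the conservative group alone and comes from the sample size for the primary endpoint. It may partly reflect missed 12-week assessments rather than unknown intervention status. The event rate is assumed; at a true 30% or more the gate is passed under evenly spread drop-out. If all of the 60% were lost by week 12, a true 25% would show as about 11%, but the Analysis Set requires at least one of V1 to V3, which raises this to about 15%. All of this stands, and it is why a range is given.
- **Little depends on it.** The study is mainly descriptive, no between-group test is planned for this endpoint, and the primary endpoint is untouched. This stands and limits the severity.

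**Conclusion.** The concern holds for two stated rules. The 20% gate contradicts the unconditional statement in the same section and leaves the crude proportion as the only assured result. Under the stated assumptions that proportion falls short of the true rate by a little over a quarter at 60% drop-out (17.9% against 25%) and by about an eighth at 25% (22.0% against 25%). Censoring event-free conservative patients at discontinuation is unsound on the literal reading (about 27 to 34% for a true 25% with 20 to 60% stopping). On the ordinary reading it is safe only if stopping is unrelated to later intervention.

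The documents do not support a general claim that the Kaplan-Meier estimate understates the rate. With non-informative loss and censoring at last contact it recovers the truth. The sizes rest on assumed event rates, exponential times, independent drop-out and an assumed 24-month horizon. This concerns one secondary, descriptive objective and is worth correcting, but it is not a must-fix.

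**What to change.** In Protocol 9.3.3, Secondary endpoints:

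1. Delete the 20% condition. State that the Kaplan-Meier cumulative incidence from 6 weeks to 24 months is always reported beside the crude counts, in line with the general methods.
2. Stop censoring at discontinuation of conservative treatment. Count interventions until the last visit or contact at which intervention status is known.
3. Use that same date for every event-free patient, including those lost or withdrawn. Do not use the end of study as defined in 5.3: it is one study-wide date, and with a 6-month inclusion period it could credit early completers with up to six unobserved months.
4. If censoring at discontinuation is wanted, report it as a sensitivity analysis and state whether later interventions count.

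The cost is wording and a little extra analysis. Treatment changes, intervention dates and study discontinuation are already collected at V1 to V5 and V-i (Table 1 and Section 6.1).

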#### **4.4.2 Study setting**

The GP examines the patient and makes the diagnosis of CVD, based on clinical signs and symptoms. Patients who receive a diagnosis of CVD according to international guidelines who require conservative or invasive treatment can be included in the study. Duplex ultrasound or any other specific examination is not required to make the diagnosis, but could be done if needed according to routine clinical practice and recommendations. Each participating GP (120 GPs) will select approximately between 10 and 15 patients with CVD.

During the inclusion visit (V0), a treatment strategy will be proposed to the patient with confirmed CVD by the GP. The treatment can be conservative or invasive, depending on the severity of the disease. Patients awaiting invasive treatment may receive conservative treatment to alleviate symptoms. The choice of treatment modality is left to the discretion of the treating physician, in agreement with the patient and according to local policies. As this is an observational study, there will be no interference in the choice of treatment, and no restrictions will be imposed.

Commonly proposed conservative treatment options include compression therapy, and oral or topical venoactive drugs. If the GP decides that the patient needs an invasive treatment, then the patient will be referred to a venous centre. The specialist to whom the patient is referred, chooses the type of invasive treatment, as done in standard clinical care. The specialist may also prescribe conservative treatment to the patient, either while awaiting invasive treatment or in case invasive treatment is not deemed necessary.

[figure not shown]
Patients and their GP may decide to switch at any time between conservative treatments or to undergo an intervention as secondary/add-on treatment to conservative treatment.

Baseline data will be collected by the GP on the day of the V0. Follow-up visits, which are expected to take place within the scope of routine clinical practice, will be organized by the GP at defined timepoints after the V0: at 6 weeks, 12 weeks, 6 months, 12 months and 24 months of follow-up (V1-V5).

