## 8. Assessment of safety

### 8.1 Specification, timing and recording of safety parameters

According to the International Conference on Harmonisation (ICH), an **AE** is any untoward medical occurrence in a subject or clinical investigation subject administered a pharmaceutical product and which does not necessarily have a causal relationship with this treatment. An AE can therefore be any unfavourable and unintended sign (including an abnormal laboratory finding), symptom or disease temporally associated with the use of a medicinal (investigational) product, whether or not related to the medicinal (investigational) product. Worsening of a pre-existing condition during the study must also be recorded as an AE.

A Treatment Emergent Adverse Event (**TEAE**) is defined as any event not present prior to the initiation of the treatments or any event already present that worsens in either intensity or frequency following exposure to the treatments.

A Serious Adverse Event (**SAE**) is defined as any untoward medical occurrence that:

- Results in death,
- Is life-threatening (the term 'life-threatening' refers to an event in which the subject was at risk of death at the time of the event; it does not refer to an event which hypothetically might have caused death if it were more severe),
- Requires inpatient hospitalisation or prolongation of existing hospitalisation,
- Results in persistent or significant disability or incapacity,
- Is a congenital anomaly or birth defect.

Pharmacovigilance data include any unintended or adverse event associated with the use of a medicinal product in humans, whether or not considered drug related, including the following special situations (situations where no AE occurred but information needs to be collected):

- Exposure during pregnancy (maternal and/or transmission of a medicinal product via semen following paternal exposure) or breastfeeding,
- Overdose, abuse, misuse, off label use, medication error, occupational exposure,
- Drug-drug or drug-food interactions,
- Any suspected transmission via a medicinal product of an infectious agent,
- Unintended therapeutic benefit,
- Lack of efficacy.

AEs and special situations will be assessed during each follow-up visit and recorded in the eCRF.

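### Secondary scores in the invasive group, timed from V0, mix untreated and treated patients at early visits, and the optional delay covariate cannot separate them

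*Protocol*

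**What the plan says.** - **Clock.** Protocol Section 4.4.2 places follow-up visits "at defined timepoints after the V0: at 6 weeks, 12 weeks, 6 months, 12 months and 24 months of follow-up (V1-V5"). This applies to all patients.
- **Wait.** The same section states: "A delay between referral to the venous centre during the V0 and the day of invasive treatment is anticipated". It adds: "Patients awaiting invasive treatment may receive conservative treatment to alleviate symptoms".
- **Primary endpoint.** Section 7 takes the invasive-group value at V-i, 12 weeks after the intervention.
- **Secondary scores.** Section 9.3.3 (Secondary endpoints) states: "The analyses will be conducted in the AS, overall and by treatment group (conservative group, invasive group"). For the quality-of-life score it plans "The change in the CIVIQ-20 GIS over time from V0 to each follow-up visit", evaluated by the methods of the primary endpoint. rVCSS and symptoms get the same treatment. CEAP change from V0 is described only. For satisfaction: "The satisfaction score over time from V1 to each follow-up visit will be described as a quantitative variable".
- **Objectives.** Objectives 3 to 7 in Section 4.1 speak of evolution by treatment. Section 4.4 gives the study's aim as assessing effectiveness.
- **Adjustment.** Section 9.1 says, without qualification, that the statistical model adjusts for the time invasive-group patients spent before their intervention. Section 9.3.3 (Primary endpoint) offers that mixed model only as a possibility. Its terms are visit as a fixed effect and the V0-to-intervention time as a covariate. The firm method is a paired t-test or a Wilcoxon signed-rank test.

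**The concern.** The protocol sees that V0 is the wrong origin for the invasive group and corrects it for one endpoint. The five repeated secondary scores stay on the V0 clock. An invasive-group mean at week 6 or week 12 is then partly a waiting-period result, possibly under conservative treatment, and partly a post-intervention result. The shape of the curve depends on how long patients wait as well as on how they do after treatment. A reader of a table headed by treatment group cannot tell the two apart.

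The one safeguard on paper is the adjustment promised in Section 9.1. If that does not work, nothing else in the analysis text of Section 9.3.3 separates the two phases for these scores.

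**Working it through.** The protocol gives no waiting time and no share treated by visit, so there is no figure of its own to reproduce here. The sample-size figure does not bear on the point.

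**1. Timing.** Let d be a patient's wait in weeks. Time since intervention is 6 − d at V1 and 12 − d at V2. A patient is at most 6 weeks post-intervention at V1 and at most 12 weeks at V2, and only if treated at about V0. Anyone with d > 6 is untreated at V1, and anyone with d > 12 is untreated at V2.

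**2. What a visit mean estimates.** Let p be the share already treated at the visit:

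mean change = p × (post-intervention change) + (1 − p) × (waiting-period change)

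The shortfall against the post-intervention change is (1 − p) × (post-intervention change − waiting-period change). The illustration below assumes a post-intervention improvement of 5 points, which is the minimum important difference in Section 9.2. The waiting-period improvement w is unknown. It is taken as 0, 2.5 or 5, because conservative treatment is allowed meanwhile.

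| p | w = 0 | w = 2.5 | w = 5 |
|---|---|---|---|
| 0.25 | 1.25 | 1.25 + 1.875 = 3.125 | 5 |
| 0.50 | 2.5 | 2.5 + 1.25 = 3.75 | 5 |
| 0.75 | 3.75 | 3.75 + 0.625 = 4.375 | 5 |
| 1.00 | 5 | 5 | 5 |

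The mean is distorted unless everyone has been treated or waiting does as well as treatment.

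**3. What p might be.** Waits were drawn from a gamma distribution (shape 4) for 600 patients. The medians are assumptions.

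| Assumed median wait | Treated by V1 | Treated by V2 | Treated by V3 |
|---|---|---|---|
| about 6 weeks | 51% | 95% | 99.8% |
| about 12 weeks | 12% | 50% | 97% |
| about 20 weeks | 2% | 15% | 70% |

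The mixing is concentrated at V1 and V2 and reaches V3 (taken as week 26) only if waits are long.

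**4. Whether the delay covariate removes it.** The model in Section 9.3.3 is, for patient i at visit j:

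score = visit effect(j) + β × delay(i) + patient effect(i) + error(i, j)

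The delay has one value per patient. In the difference between visit j and V0 for the same patient, β × delay(i) cancels. With complete data the visit estimates therefore equal the raw mean changes whether or not the covariate is present. No term says whether a visit fell before or after the intervention, and there is no visit-by-delay term.

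The check used the same 600 patients with complete data and a true change of −5 after the intervention and 0 before it (a fall in score is an improvement). In every scenario the visit estimates agreed to three decimals with and without the covariate. At V2 with a median wait of about 12 weeks, both were −2.532. The mixture formula predicts 0.498 × (−5) = −2.49, so the covariate left the dilution in place.

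**5. Which scores have any adjustment.**

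| Score | Planned method | Adjustment for the wait |
|---|---|---|
| CIVIQ-20 GIS, rVCSS, symptoms | paired test; mixed model optional | none in the paired test; the optional covariate is ineffective |
| CEAP, satisfaction | descriptive | none |

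**The case against.** **The protocol does address the wait.** Section 9.1 promises an adjustment, and the secondary text carries the primary methods over to three scores. This stands as a statement of intent. It fails in execution, because the model is optional and its covariate does not separate the phases.

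**V-i may count as a follow-up visit.** Section 4.4.2 calls it one, and all five scores are collected there, so an intervention-timed value at 12 weeks will exist for many patients. That is a fair point. But V-i is one time point, held only where routine practice allows, and it replaces any scheduled visit it overlaps. The secondary text names no V-i analysis of these scores, and V1 and V2 remain mixed.

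**Group rules are left to the SAP.** True, and the SAP could help. The origin of the change scores and the form of the covariate are fixed in the protocol.

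**A V0 clock is legitimate.** It describes the course after the treatment decision on the same footing as the conservative group. This stands, so the V0-based summary can be kept. It should not be the only one.

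A reader might also infer more than the documents support:

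- *That every secondary outcome is affected.* Time to re-intervention is counted from the intervention date.
- *That all five scores are tested, or that early means are reported as the effect of invasive treatment.* CEAP and satisfaction are described only. The analyses are called mainly descriptive, and the objectives speak of evolution.
- *That adverse events during the wait are charged to the intervention.* Section 8.1 defines treatment-emergent events by reference to "any event not present prior to the initiation of the treatments", and Section 8.2 records the start date and the relationship to treatment.
- *That most of the group will be untreated at weeks 6 and 12.* The protocol gives no waiting times.

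**Conclusion.** The point holds for the five repeated secondary scores in the invasive group. Timed from V0, their early results, chiefly V1 and V2, combine not-yet-treated and treated patients under objectives about evolution by treatment. Section 9.1 and the primary-endpoint paragraph of Section 9.3.3 disagree on whether an adjustment will be made. The adjustment described would not work in any case. Its exact lack of effect on visit estimates is shown for complete data. With missing visits the estimates could shift somewhat, but the model would still hold no information on treatment status at each visit.

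The size is unknown. It is (1 − p) times the gap between post-intervention and waiting-period change, and the protocol gives neither p nor that gap. With an assumed 5-point gain and none while waiting, the shortfall is 2.5 points at p = 0.5 and 3.75 at p = 0.25. It vanishes if everyone has been treated by the visit or if the wait brings the same change. The primary endpoint at V-i is not touched by this point. It should be corrected before the analysis.

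**What to change.** 1. Reconcile Section 9.1 with Section 9.3.3: state whether the model is planned or optional, and for which scores.
2. In the invasive group, classify each V1 to V5 record as before or after the intervention. Intervention dates are already collected (Section 4.6, note c to Table 1).
3. Report pre-intervention records as a separate waiting phase and post-intervention records by time since intervention, including V-i for all five scores. Keep the V0-based summary alongside if wanted, labelled as the course since inclusion.
4. In the mixed model, replace the fixed delay covariate with a time-varying before/after status or with time since intervention.
5. Report satisfaction ratings given before the intervention separately from those given after it. Early ratings are not discarded, since they may concern conservative care during the wait.
6. Show the distribution of waiting times and the share treated at each visit, so that readers can judge the mixing in any V0-based table.

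The cost is wording and programming, with no new data collection. The downside is fewer patients per post-intervention time point, and shorter post-intervention follow-up for patients with long waits, because the study ends on the V0 clock.
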